10.3.3.3. Area of Autograft in DPT Wounds

For each DPT target wound, percent area wound autografted will be calculated as the sum of areas autografted in all autografting procedures of the specific wound, as collected on CRF wound management page (field "% area wound grafted clin. ass."). Treated DPT target wounds that had not been autografted will receive the value of 0.

For the purpose of the Main analysis, percent area wound autografted will be calculated on a subject level.

For each subject with at least one DPT target wound, the percent area wound autografted in DPT wounds will be calculated as follows:

$$TBSA\ Autograft\ in\ DPT = \frac{\sum_{i} TBSA_{i} * \%Autograft_{i}}{\sum_{i} TBSA_{i}}$$

where $TBSA_i$ is the % TBSA of the ith DPT target wound (the original TW assessment defined in the treatment visit), $\%Autograft_i$ is the corresponding percent area autografted of that wound and the sum is taken over all DPT target wounds of a patient.

This is a weighted average of the % area autografted over all DPT target wounds for that patient, and is equivalent to the formula:

$$\textit{TBSA Autograft in DPT} = \frac{\sum_{i} areaAutografted_{i}}{\sum_{i} \textit{TBSA}_{i}} * 100\%$$

where $areaAutografted_i$ is the area autografted in the ith DPT target wound.

Patients with only FT wounds and having no DPT wounds will be excluded from this analysis.

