- 3. Reduction in the need for autograft Percent area of deep partial thickness wounds autografted
- 4. Reduction in the need for autograft Incidence of autograft performed in deep partial thickness wounds

Safety Outcome Measures:

- 1. Time to reach complete wound closure assessed in days, starting from randomization date
- 2. Cosmesis and Function- will be measured using MVSS, to demonstrate that treatment with NexoBrid does not have any clinically meaningful deleterious effect on burns scars quality as compared to the quality of burns scars treated with SOC, measured at 12 months from wound closure date, by a blinded assessor.
- 3. Cosmesis and Function- will be measured using MVSS, to demonstrate that treatment with NexoBrid does not have any clinically meaningful deleterious effect on burns scars quality as compared to the quality of burns scars treated with SOC, measured at 24 months from wound closure date, by a blinded assessor.
- 4. Additional Safety Outcome Measures:
 - a. General parameters: Systemic adverse events, vital signs, pain assessment (using FPS-R and as reported as AEs), laboratory tests, units (and volume) of blood transfusion given during hospitalization, Immunogenicity evaluation for NexoBrid patients, Pyrexia and Hyperthermia, Systemic infections, Extent of antibiotic use (i.e. number of days of exposure), Rates

Protocol: MW 2012-01-01	Version 11.01- 16 Jun 2021	Page 7 of 10

of hospital readmission, Change in INR/PTT and incidence of change to > upper limit of normal (after treatment), Change in blood glucose and incidence of change to above upper limit of normal (after treatment).

- b. Long term functionality evaluation of the extremities using the 'Lower Extremity Functional Scale', 'QuickDASH' questionnaires and 'Range Of Motion' measurements,
- c. Long term Quality of Life using EQ5D and BOQ for a subset of patients.
- d. Local parameters: Local adverse events defined by treating physician or designee; graft loss, wound related infections, etc.

Exploratory Endpoint

- 1. Incidence of surgical escharotomy procedures on circumferential extremities target wounds,
- 2. Incidence of reduction in interstitial/compartment pressure in circumferential extremity wounds (measured immediately following eschar removal),
- 3. Reduction in surgical needs as measured by an analysis of % wound area surgically excised for eschar removal.

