7.2.2.2. Secondary Endpoints

The following secondary endpoints will be evaluated in this study and compared between NexoBrid and SoC:

Incidence of Surgical Excision

Reduction of surgical need for excisional eschar removal is measured by an analysis of incidence (yes/no response) of surgical eschar removal (tangential/ minor/ avulsion/ Versajet and/or dermabrasion excision). The time frame for this incidence rate is until complete eschar removal has been achieved.

Blood Loss

Blood loss incurred during the eschar removal procedures will be evaluated. Actual blood loss will be measured by considering the estimated blood loss, changes in Hematocrit during the eschar removal procedures and the amount of units of blood transfused. Blood loss will be calculated using the following formula [15]:

$$Blood\ Loss\ (mL) = \frac{RBCV_{before} + (Transfusion\ RBCV) - RBCV_{after}}{Hct_{after} [\%] * 0.01}$$

RBCV (mL) = Red Blood Cell Volume (mL) = Body Weight (kg) * 80 (mL/kg) * (Hematocrit [%] * 0.01)

Transfusion RBCV (mL) = [Total Volume (mL) of Whole Blood Transfused * 0.3] + [Total Volume (mL) of Packed Red Blood Cells Transfused * 0.8]

The blood loss will be computed over the whole eschar removal period, using the formula above, i.e. the eschar removal process will be considered as one continuous procedure. Therefore, only the Hematocrit value before the first eschar removal procedure and after the last procedure will be used and all blood transfusions performed between these measurements will be included.

Additionally, the blood loss will be summed over all procedures carried out to remove eschar, with the hematocrit measured immediately before each procedure and 4 hours after its completion. The amount of blood transfused will be summed over all transfusions carried out during the debridement procedure and up to 24 hours from the end time of the debridement procedure.

Analyses with both blood loss values will be conducted. However, some missing values are expected. The analysis with less missing values will be regarded as more reliable and is therefore considered the main analysis. The other analysis is considered supportive.

Area of Autograft in DPT Wounds

Reduction in the need for Autograft in deep partial thickness wounds is measured by an analysis of percent area of deep partial thickness wounds autografted.

Incidence of Autograft in DPT Wounds

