9.1.2. Secondary Endpoint: Incidence of Surgical Excision

Estimated proportions having surgical excision from study MW2004-11-02: NexoBrid 0.42; SoC 0.80

Standard errors: NexoBrid 0.057; SoC 0.044

Difference = 0.38; Standard error of difference = 0.073

Anticipated difference: 0.38-0.073/2 ≈ 0.34

We therefore take the anticipated proportion with surgical excision to be: NexoBrid 0.44 and SoC 0.78.

Using Fisher's exact test, the power achieved with a total sample size of 160 patients (80 in each group) using a two-sided significance level of 5% is 99.1%.

Statistical Analysis Plan V02 of 31 May 2021

⁵ Updated calculations were performed to support the final sample size of 145 patients enrolled into the study (provided in 13.3 13.3Update to Study Sample Size Due to COVID-19 Pandemic)

9.1.3. **Secondary Endpoint: Blood Loss**

Estimated mean blood loss from study MW2004-11-02: NexoBrid 421.93 ml; SoC 1024.27 ml

Standard errors: NexoBrid 129.52; SoC 240.98

Difference: -602.33; Standard error of difference: 273.58

Anticipated difference: -602.33 + 273.58 / 2 = -465.54

Using a two-sided two-sample t-test the power with a total sample size of 160 patients and a two-sided significance level of 5% is 58.8%.

Secondary Endpoint: Area of Autograft in DPT Wounds

The proportion of subjects with at least one DPT wound was 62.6% in the study MW2004-11-02. Therefore, if 160 patients are enrolled to the CIDS study, we expect 100 patients to have at least one DPT wound and be thereby eligible for this analysis.

Estimated difference in mean area autograft in DPT wounds from study MW2004-11-02 (NexoBrid vs. SoC) = 13.30-23.63 = -10.33.

Standard error = 6.02

Target difference $\Delta = -10.33 + 6.02/2 \approx -7.32$.

Using a two-sided two-sample t-test the power with a total sample size of 160 patients using a two-sided significance level of 5% is 23.1%.

Secondary Endpoint: Incidence of Autograft in DPT Wounds

Estimated log OR using GEE approach from study MW2004-11-02 (NexoBrid vs SoC): -0.676

Standard Error: 0.40

Anticipated log OR: -0.676+0.40/2=-0.476

Using the normal approximation to the Wald test statistics (see for example Shih (1997)) we obtain a power of 53.3% with a total sample size of 160 patients using a two-sided significance level of 5%.

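### The percent area autografted is an uncapped sum over procedures, so repeat grafting can push a wound above 100% and mixes extent of grafting with re-grafting

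*SAP*

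**What the plan says.** The Protocol synopsis lists the third secondary endpoint, under reduced need for autograft, as "Percent area of deep partial thickness wounds autografted". SAP Section 7.2.2.2 describes it the same way: "percent area of deep partial thickness wounds autografted".

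SAP Section 10.3.3.3 makes this operational. The wound-level rule, which applies to DPT target wounds only, reads: "percent area wound autografted will be calculated as the sum of areas autografted in all autografting procedures of the specific wound". The input is a CRF field on the wound management page that records the percentage of the wound grafted. Treated wounds without a graft score 0. The patient value weights each wound by its original %TBSA: "This is a weighted average of the % area autografted over all DPT target wounds for that patient". The section gives a second form of the formula, total area autografted over total wound area, and calls the two equivalent.

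Section 10.1.3.3 analyses the patient value by linear regression after multiple imputation and bounds neither observed nor imputed values. Section 11.1.9 places the endpoint fourth of five in the hierarchy, ahead of incidence of autograft.

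No section caps the sum, or separates a second graft on the same area from staged grafts on different areas. Graft loss is foreseen: the Protocol's local safety parameters include "graft loss, wound related infections, etc".

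**The concern.** On its ordinary reading, a percentage of wound area autografted runs from 0 to 100. The rule is the right measure when different parts of a wound are grafted in stages. It is not when the same part is grafted again: the second graft adds to the numerator while the denominator stays at the original wound area. The equivalence stated in 10.3.3.3 then holds only if area autografted is read as cumulative area, which the text does not say.

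At stake is what a result in step 4 means. Two arms with identical skin area needing a graft could differ on this endpoint because grafts were repeated more often in one of them. The result also decides whether step 5 is tested.

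**Working it through.** **1. The plan's own figure.** SAP Section 9.1.4 gives a prior difference of "13.30-23.63 = -10.33" and "Standard error = 6.02", hence a target of -10.33 + 6.02/2 = -7.32 points, and a stated power of 23.1% with 160 patients, of whom 100 are expected to have a DPT wound.

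The SD is not stated and has to be inferred. The wound-level calculations in Appendix 13.3 imply the number of evaluable patients in the earlier study:

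- Area: 304 / (4.89 × 3.24 / 8.97)² ≈ 97
- Incidence: 720 / (0.40 × 3.24 / 0.476)² ≈ 97

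Assuming equal arms, SD = 6.02 / √(4/97) = 29.65. A two-sided 5% t-test with 50 per arm then has 23.1% power, which reproduces the plan. At the final 145 patients the same inputs give about 21.4% (62.6% evaluable) or 20.1% (58% evaluable, the share in the second earlier study).

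**2. Evaluable patients per arm (n).** 160 × 0.626 / 2 = 50; 145 × 0.626 / 2 = 45; 145 × 0.58 / 2 = 42.

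**3. Shift from re-grafting.** If a net excess of k patients in one arm each have a further e% of their DPT area counted again, the arm mean moves by k × e / n. For one patient with e = 100 this is 2.0, 2.2 or 2.4 points at n = 50, 45 or 42. At n = 45 that is 2.2 / 7.32 = 30% of the target.

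The net excess that equals the target is k = 7.32 × n / e:

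| Extent e | n = 50 | n = 45 | n = 42 |
|---|---|---|---|
| 100% | 3.7 | 3.3 | 3.1 |
| 50% | 7.3 | 6.6 | 6.2 |
| 25% | 14.6 | 13.2 | 12.3 |

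The extents are assumptions; the documents give neither rate nor extent.

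**4. The same shift as a share of grafted area.** Against the earlier study's means, 7.32 / 23.63 = 31% of all SoC grafted area, or 7.32 / 13.30 = 55% of all NexoBrid grafted area, would have to be re-grafted, with none in the other arm.

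**5. Illustrative simulation.** Assumptions: 50 per arm, 36% (SoC) and 25% (NexoBrid) of patients grafted, grafts covering 30 to 100% of area, ordinary t-test, true difference about -7.3. Rejection was 20 to 22% without re-grafts. Four full repeats of the original graft in SoC only gave a difference of -12.7 and 36% rejection; four in NexoBrid only gave -2.1 and 3%. With no true difference, four full repeats in SoC only gave 7.2% rejection, against about 5% without.

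**6. What a cap does.**

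| Grafts on one wound | Sum | Capped | Area grafted at least once |
|---|---|---|---|
| 100%, same 100% again | 200 | 100 | 100 |
| 60%, same 60% again | 120 | 100 | 60 |
| 40%, same 40% again | 80 | 80 | 40 |
| 50%, then the other 50% | 100 | 100 | 100 |

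The area grafted at least once never exceeds the capped value, and the capped value never exceeds the sum. The cap is therefore never further from the labelled quantity than the sum is, but it is only an upper bound.

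**The case against.** The strongest defence is that the sum is a choice of estimand. The endpoint is headed as need for autograft, the rule openly covers all procedures, and cumulative grafting is a defensible measure of need. A systematic difference in re-grafting would also be a real treatment effect. This stands as far as it goes, and is why the cumulative sum should still be reported. It does not make a value above 100% a percentage of wound area, and neither document says that cumulative grafting is intended.

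A reader might infer that any re-grafted wound scores above 100%. It does not: 60% followed by 20% gives 80%, although the same area may be counted twice.

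A reader might also infer that a few graft failures could create or erase the target difference. The documents do not support that in general. It needs re-grafts of nearly the whole DPT area, concentrated in one arm; no rate is given; and balanced re-grafting mainly adds variance. The re-randomization p-value (SAP Section 11.1.2) also gives protection against chance imbalance in a few extreme values.

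Other points stand too. The earlier means may already rest on a summed definition; the documents do not say. Incidence of autograft is scored yes or no per wound and cannot be inflated by re-grafting. The endpoint is weak in any case, with 23.1% stated power. None of these settles what the area endpoint measures.

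**Conclusion.** The concern holds as a defect of definition. The rule in 10.3.3.3 allows values that are impossible for the endpoint as labelled, and it mixes extent of grafting with repeat grafting. The practical size is unknown. A target-sized shift takes a net excess of 3 to 4 patients with whole-area re-grafts in one arm, 6 to 7 at 50% extent, or 12 to 15 at 25%. These counts assume 42 to 50 evaluable patients per arm and take the 7.32-point target as the benchmark. The primary endpoint and the first two secondary endpoints are not affected. The definition should be corrected because the endpoint is part of the confirmatory hierarchy, but nothing in the documents shows that the result will be materially distorted.

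**What to change.** In SAP Section 10.3.3.3:

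- State that the main endpoint is the share of wound area grafted at least once, with each wound's value limited to 100%.
- Where the CRF identifies a re-graft of an already grafted area, do not count that area again; sum only staged grafts of different areas.
- Acknowledge that where the CRF cannot separate the two, the capped value is an upper bound and leaves double counting below 100%.
- Prespecify the uncapped cumulative sum as a sensitivity analysis, so that re-grafting need stays visible.

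The cap costs a short text change and one line of code. Identifying re-grafts costs more, because it depends on what the CRF records, and the documents do not show that. The downside is that repeat grafting leaves the main analysis.

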10.3.3.4. Incidence of Autograft in DPT Wounds

For each DPT TW a binary (yes/no) variable will be defined, indicating whether this wound needed autografting.

10.3.4. Safety Endpoints

10.3.4.1. Time to Reach Complete Wound Closure

Information about date will be transformed to time in days from randomization. Missing values will be addressed as described in Section 10.1.4.1.

For the purpose of the main analysis, time until complete wound closure (for definition see Section 6.1), will be defined as the time (in days) until complete wound closure has been achieved at a wound level. The definition of complete wound closure demands that the wound closure is to be confirmed at two consecutive study visits, 2 weeks, i.e. 14 (± 2 days), apart. A wound is only to be regarded as closed in this analysis if the wound was closed at a wound closure assessment and this was confirmed at an additional assessment within 12-16 days from the initial closure assessment. In case wound closure is not confirmed in the pre-defined time frame the wound is considered not completely closed at the first closure assessment.

Additionally, for the SoC group, a variable for time to wound closure will be calculated as above, but in the non-inferiority comparison, a 7 days non-inferiority margin will be added.

For additional analyses on a subject level, time to complete wound closure of all target wounds (last healing wound) will be computed, i.e. the time from randomization (in days) to subject's last wound closure.

For supportive analyses, the time to reach 100% wound closure will be computed on a wound level and on a subject level, where the complete wound closure is defined as 100% of wound area epithelialized and/or closed by graft without drainage or dressing requirements confirmed at two consecutive study visits, 2 weeks apart.

10.3.4.2. Cosmesis and Function at 12 Months from Wound Closure

MVSS sub scores at 12 months for pigmentation, pliability, height, vascularity, pain and pruritus will be added up to obtain the overall MVSS score (range 0 to 18) at 12 months per target

wound. The patient MVSS score will be the average of the MVSS over all TWs. To note, in case the individual item score is missing, the TW score and the patient score will be defined as missing.

10.3.4.3. Cosmesis and Function at 24 Months from Wound Closure

MVSS sub scores at 24 months for pigmentation, pliability, height, vascularity, pain and pruritus will be added up to obtain the overall MVSS score (range 0 to 18) at 24 months per target wound. The patient MVSS score will be the average of the MVSS over all TWs. To note, in case the individual item score is missing, the TW score and the patient score will be defined as missing.

10.3.4.4. General Parameters of Safety

Volume of Blood Transfusions Given

The volume of blood transfusions given during hospitalization (including readmissions) will be according to the volume (in milliliters) of whole blood and packed red blood cells transfused, presented separately, as collected on eCRF. In addition, Transfusion RBC Volume (in milliliters) will be calculated using the following formula [15], [48]:

Transfusion RBC Volume (mL)

- = $[Total\ Volume\ (mL)\ of\ Whole\ Blood\ Transfused \times 0.3]$
- + [Total Volume (mL) of Packed Red Blood Cells Transfused \times 0.8]

For subjects who discontinued study participation during the efficacy assessment period, it is not known whether a(nother) transfusion occurred and relevant data are missing. Consequently, the variable is set to missing for all those subjects except for "Lost-to-follow-ups" who completed the eschar removal treatment. The exception is done under the assumption that subjects who are lost to follow up would have come back for readmission if this had been necessary (see also safety endpoint "rates of hospital readmission").

Analgesia and Anesthesia

Relevant analgesia and anesthesia medications will be presented in the concomitant medications tables.

Antibiotic Use

The number of days of exposure to systemic antibiotic drugs will be calculated for each patient. This will be done overall and also for antibiotic use due to AE involvement (as indicated in the eCRF) and for prophylactic antibiotic use (as indicated in the eCRF) separately.

Only records with ATC level 2 equal to "ANTIBACTERIALS FOR SYSTEMIC USE" are used. In case of a missing start date for a medication marked as pre-existing, the start date is imputed by the date of informed consent. In case of a missing stop date for a medication ongoing at study termination, the stop date is imputed by the study termination date. No other imputation is planned, i.e. if the start or stop date for antibiotics is missing, the days of antibiotic use will be counted as missing for the respective subject.

The calculation of the number of days only considers days between randomization and wound closure confirmation. Each day is only counted once; the actual frequency is not considered. Values for subjects with premature study discontinuation prior to the end of the efficacy assessment period are set to missing.

Rates of Hospital Readmission

For each patient a binary (yes/no) variable will be computed indicating whether this patient had a hospital readmission or not. Additionally, for each hospital readmission, a binary (yes/no) variable will be collected indicating whether this readmission was planned or not. A readmission will be considered as being planned when the reason for readmission was indicated as "planned wound management" or "scar modulation" in the eCRF. Readmissions for which the reason was given as "AE" in the eCRF are considered as being unplanned. Hospital readmission for which the reason is given as "other" will be reviewed by the sponsor in order to decide whether they are to be classified as planned or unplanned.

Furthermore, a variable giving the number of planned hospital readmissions and a variable giving the number of unplanned readmissions will be computed for each patient.

Relative and absolute frequencies of hospital readmission (overall, planned, and unplanned) will be calculated per treatment arm.

For subjects who discontinued study participation during the efficacy assessment period, it is not known whether a(nother) readmission occurred and relevant data are missing.

Consequently, the variable is set to missing for all those subjects except for "Lost-to-follow-ups" who completed the eschar removal treatment. The exception is done under the assumption that subjects who are lost to follow up would have come back for readmission if this had been necessary (Without this exception a lot of information would have been lost in MW2010 since the percentage of subjects with re-admission is higher for "Lost-to-follow-ups" then for the rest of the population).

Change in PTT/INR

Change in PTT/INR will be computed as PTT/INR on $4h \pm 15$ min post first application (NexoBrid arm) respectively to 4h post first SoC treatment (SoC arm) minus PTT/INR pre the respective procedure for each patient.

For the classification of normal and abnormal PTT/INR values (low or high), the reference limits of the local labs will be used. If INR reference ranges will not be available for specific sites, common normal range of 0.8-1.2 will be used for these sites [19].

In addition, for each subject, for each parameter (INR/PTT) a variable will be computed, indicating whether the 4 hour post first treatment measurement was post treatment potentially clinically significant high (pCS high) or post treatment potentially clinically significant low (pCS low).

For the definition of pCS high and pCS low, see Section 13.2.2.

Lower Extremity Function Scale (LEFS)

The LEFS will be assessed at the following time points: at 6, 12 weeks and months 6, 12, 18 and 24 after wound closure. It consists of 20 items which can each be answered on a scale of 0 to 4. In the database the answers will be coded as 1 to 5. Therefore, the total LEFS for a patient will be computed as

$$LEFS = \sum_{i=1}^{20} a_i - 20,$$

where a_i is the answer to item i (coded 1 to 5). As indicated in Section 10.1.4.4, the calculation of the total score will be made if less than or equal to 10% of the items were left blank. If more than 10% of items are missing the score cannot be calculated. In the event of missing

items, the total score will be adjusted by dividing the total by the proportion of completed items, as follows:

$$LEFS = \frac{\sum_{i=1}^{k} a_i}{k/20} - 20$$

where k is the number of completed items and a_i are the non-missing values.

Disabilities of the Arm, Shoulder and Hand (QuickDASH)

The QuickDASH will be assessed at the following time points: at 6, 12 weeks and months 6, 12, 18 and 24 after wound closure. It consists of 11 items which are scored 1-5. As indicated in Section 10.1.4.4, the calculation of the total score will be made if less than or equal to 10% of the items were left blank. If more than 10% of items are missing the score cannot be calculated. Hence, at least 10 of the 11 items must be completed for a score to be calculated. The assigned values for all completed responses are simply summed and averaged, producing a score out of five. This value is then transformed to a score out of 100 by subtracting one and multiplying by 25. Hence, the QuickDASH score for a single patient is calculated by:

$$QuickDASH = \left(\frac{sum\ of\ n\ responses}{n} - 1\right) * 25.$$

Range of Motion (ROM)

For each visit (12 months FU and 24 months FU), a binary (yes/no) variable will be calculated, indicating whether the range of motion assessment for that patient was abnormal or not. The range of motion assessment will be considered abnormal, if the measurement of at least one joint under consideration does not lie within the normal ranges of motion given in appendix 13 of the study protocol at the respective time point. For handling of missing data see Section 10.1.4.4.

EQ-5D (Quality of Life)

EQ-5D-Y consists of 5 items with 3 possible answers each. It will be evaluated per the EQ-5D-Y user guide [20]. Note that for children aged 2 – 11 years, the parent/caregiver will complete a proxy version of the EQ-5D for the patient, children aged 12-18 will complete the

questionnaire themselves. EQ-5D will not be assessed for children younger than 2 years (based on age of first FU visit).

For each item, relative and absolute frequencies of the answers will be computed in total and per age group, defined in the stratification variables (see Section 11.1.11). The table will be presented by treatment arm and overall. The analysis will be done per age at randomization. Furthermore, summary statistics of the EQ VAS will be computed in total and per age group. The table will be presented by treatment arm and overall.

The EQ-5D states will be converted to a single summary index using the USA value set from [21]. For subjects with incomplete questionnaires, the summary index will be a missing value.

Immunogenicity Evaluation

The immunogenicity evaluation will be done in a separate analysis and is described in a separate document.

Pyrexia and Hypothermia

Pyrexia (and related terms) and hypothermia reported as AEs will be presented in the AEs tables.

Systemic Infection

Systemic infections reported as AEs will be presented in the AEs tables.

Adverse Events

Counts and frequencies of subjects reporting treatment emergent adverse events (TEAEs), related TEAEs, and serious TEAEs per treatment arm will be computed per system organ class (SOC) and preferred term (PT). This will be done separately by:

- Severity (mild / moderate / severe AEs)
- Relatedness (not related or remotely related / possibly related or probably related or related AEs)

Time of onset (during the treatment session / within 24 hours after treatment / 24 – 72 hours after treatment / more than 72 hours up to the end of the first week after treatment / during week 2 to week 4 after treatment / more than 4 weeks after treatment)

Note: During the treatment session is defined as the time frame from start date/time of first eschar removal procedure to end date/time of last eschar removal procedure.

All serious adverse events will be listed for the enrolled population.

For more details see Section 11.1.5.4.

For each of the two stages of analysis (see Section 11 for details), the safety data gathered in that stage will be analyzed separately. That is, in the first stage analysis (acute + 12M follow-up), all AEs reported until the 12 months follow-up will be analyzed separately for the following sub-periods: 1) until the 12 weeks follow-up, 2) between the 12 weeks follow-up and the 12 months follow-up (including AEs from the first sub-period that are still ongoing), 3) combined until the 12 months follow-up. In the second stage analysis (24 months follow-up), all AEs reported between the 12 months follow-up and the 24 months follow-up (including AEs from the first stage that are still ongoing) will be analyzed. Furthermore, a combined analysis, including all reported AEs, will be provided at the end of the trial.

Central Laboratory Values

For all analyses involving data from the central laboratory only samples taken within the allowed time range are considered

- Pre procedure: Within 12 hours before start of the procedure until up to 15 min after start.
- Post procedure: Within 24 hours after end of the procedure

Samples not taken in the allowed time range are excluded from the analysis.

Imputation of data from the central laboratory is only done for planned missing values. Version 10.01 of the study protocol specifies some planned missing laboratory samples. On the one hand, a laboratory sample before the additional application of NexoBrid is not required. On the other hand, a laboratory sample before a nonsurgical procedure is only prescribed for the first eschar removal procedure and a laboratory sample after a nonsurgical procedure is only

required for the last eschar removal procedure. To enable analysis of pre-post differences on procedure level, the planned missing values are imputed as follows:

- Planned missing measurements before an additional application / a non-surgical procedure
 - Values of a sample taken after the previous eschar removal procedure are used if the laboratory sample was taken within 12 hours before start of the eschar removal procedure.
- Planned missing measurements after a non-surgical procedure
 Values of a sample taken before the subsequent eschar removal procedure are used if the laboratory sample was taken within 24 hours after end of the nonsurgical procedure.

For each subject, each laboratory parameter and each time point of measurement a variable will be defined, indicating whether this measurement was post treatment potentially clinically significant high (pCS high) or post treatment potentially clinically significant low (pCS low).

From this, for each subject and each laboratory parameter, an indication whether this subject experienced any pCS high measurement post baseline in this parameter and/or whether this subject experienced any pCS low measurement post baseline in this parameter will be produced.

For the definition of pCS high and pCS low, see Section 13.2.2.

Vital Signs

Body temperatures given in °F will be transformed to °C using the following formula:

$$Temperature[°C] = \frac{5}{9}(Temperature[°F] - 32)$$

Differences in the vital signs assessments (body temperature, heart rate, respiratory rate, systolic blood pressure, diastolic blood pressure) between daily visits will be calculated by

$$Diff_d = VS_d - VS_{d-1}$$

where VS_d is the vital sign assessment at day d (daily follow-up) and d is varied from 2 to 7.

Note: Vital sign assessments will only be recorded while a subject is hospitalized. It may however be the case that certain subjects will be discharged during the first week, making some of the measurements not available. The respective subjects will be excluded from all vital sign analysis referring to time points after hospital discharge.

Additionally, for each subject, each vital sign and each time point of measurement a variable will be defined, indicating whether this measurement was post treatment potentially clinically significant high (pCS high) or post treatment potentially clinically significant low (pCS low) (based on definitions in Section 13.2.1). Baseline categories (pCS low, pCS high and not pCS) will be created using the reference values from Section 13.2.1 without the increase/decrease criteria.

In addition, for each subject and each vital sign an indication whether the subject experienced any pCS high and/or any pCS low result post baseline (within the first 7 days) in this vital sign will be produced.

For subjects discharged before day 7, this indication will be calculated only taking into account the time during hospitalization.

Pain Assessment

Pain assessments will only be recorded while a subject is hospitalized. It may however be the case that certain subjects will be discharged during the first week, making some of the measurements not available. The respective subjects will be excluded from all pain analysis referring to time points after hospital discharge.

For each eschar removal procedure and each daily follow-up pain assessment the change in pain from baseline will be calculated as

$$Diff_d = Pain_d - Pain_{Base}$$

where $Pain_d$ is the pain assessment at the respective time point. For the calculation of the difference in pain for the eschar removal procedures the pain assessment post that procedure will be used. The pain value captured pre first procedure will be considered as baseline. If this is missing, the pain assessed at screening will be used.

In addition, for each patient, an indication will be produced whether:

- The patient experienced any post treatment abnormal (NCS) pain assessment according to investigator's assessment
- The patient experienced any post treatment abnormal (CS) pain assessment according to investigator's assessment

For subjects discharged before day 7, this indication will be calculated only taking into account the time during hospitalization.

